**FORM: Application for Human Research**

NUMBER	FORM DATE	PAGE
F200		18 of 18

Submitting documents to the IRB

All materials must be typed and submitted electronically. Maintain electronic copies of all information submitted to the HSPP office in case revisions are required. It is recommended that version dates be used while naming documents.

1. Documents must be submitted to the [contact] account and not to individual staff email accounts. After contact by a staff member future correspondence may be communicated directly to the staff member concerning the submission.
2. **If acknowledgement of receipt is needed, please request a "Read Receipt" through your email server.** If you use Microsoft Outlook 2007, this is accomplished by clicking "Options" and choosing the "Request a Read Receipt" checkbox in a new email.
3. One submission request per email (e.g. one new project submission, one continuing review plus attachments, or one modification request).
4. All submissions must have signatures. An email acknowledgement in place of a signature will not be acceptable. If electronic signatures are not available for use, the signature pages may be signed and scanned as a separate Adobe PDF document and attached to the submission email.
5. **Microsoft Word documents are REQUIRED** for (applications, consents, recruitment materials, and data collection instruments (if available). PDFs may be submitted for documents that typically are not revised by the IRB (e.g. Investigator Brochures, sponsor protocols).
6. The email subject line must include: IRB # (if assigned one), PI Last Name, and type of submission (Modification, New Project, Continuing Review, Reportable Item, etc.).
7. The email must provide a list of the documents submitted for review. While the documents attached do not have to adhere to a specific naming scheme, it is requested that each document be named to clearly reflect what is inside.

Submissions not following these guidelines will be returned without review

## Statistical Approach

- Pain Reduction:

Pain level at the plantar fascia was self-reported by subjects at pre-treatment (used as baseline measurement) and again at each follow-up - 4, 8, 12, and 26 weeks - after initial treatment. The pain scale subjects used to identify their level of pain was a 10-point pain scale range, where 0 = no pain, 1 = slight pain through 10 which equates to the patient's worst imaginable pain. The goal for all subjects in the treatment group was to reduce pain by at least 25%. Pain scores reported at follow-up timepoints were compared to baseline score for each subject to determine if the goal was met by dividing the difference in the follow-up and baseline pain score by the baseline pain score. The percentage of subjects that met the pain reduction goal was calculated at each timepoint for both control/sham-treated and treatment groups by dividing the number of subjects that achieved the pain reduction goal at each timepoint by the total number of patients that gave a pain score for that time point.

- Plantar Fascia Hypoechoic Lesion Size:

A large proportion of patients suffering from chronic plantar fasciitis present with hypoechoic lesions in or around the proximal plantar fascia, as viewed by diagnostic ultrasound imaging[7].

Hypoechoic lesions were imaged and volumes were calculated at the baseline visit and each follow-up visit by measuring the inferior-to-superior and posterior-to-anterior radii in the long axis and the medial-to-lateral radius of the transverse axis and applying the following formula for the volume of an ellipse:

$$\text{Volume} = (4/3)\pi \cdot r_1 \cdot r_2 \cdot r_3$$

With  $r_1$ ,  $r_2$ , and  $r_3$  representing the three radii detailed above. Changes to lesion volumes were recorded at each follow-up timepoint and compared to baseline by dividing the volume of the lesion at that timepoint with the volume of the same lesion at pre-treatment baseline.

- Foot Function Index Score Reduction:

In addition to the 11-point VAS pain scale, patients self-reported answers to questions from the Foot Function Index (FFI) pain subscale questionnaire, which has been standardized in a number of PF-focused publications [8-10]. Scores range from 0-90, with 0 indicating no pain and 90 indicating the worst pain imaginable in a variety of daily activities involving use of the plantar fascia. Self-reported scores were taken at baseline and each follow-up timepoint. The average score for each timepoint were calculated, and follow-up averages were compared to baseline to calculated the percentage reduction in score.

- Statistical Calculations

Student T-tests were utilized to determine statistically significant differences between baseline and subsequent follow-up measurements for self-reported and lesion size measurements. The level of significance ( $\alpha$ ) was set to 0.05.

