**FORM: Application for Human Research**

NUMBER	FORM DATE	PAGE
F200		8 of 18

3) Setting of the Human Research

The PI is an assistant professor in the Department of Orthopaedic Surgery and surgeon with the University of Arizona Health Network. Subjects will be recruited from the outpatient clinic of Drs. [name] (PI) and [name]. The age, gender, height, weight, activity level, pain level, and physical exam findings of patients will be obtained directly from the subject, the subject's medical record, or from direct examination and then recorded in a password protected excel file. The online survey can be completed from any computer available to the subject. Intense therapeutic ultrasound and diagnostic ultrasound will be administered in the Human Movements Biomechanics Lab (BRL B101).

4) Resources available to conduct the Human Research

Equipment for intense therapeutic ultrasound will be provided by [name] and [name] from Guided Therapy Systems. The equipment for measuring height and weight will be in the orthopedic clinic. Personnel available to conduct the study include 2 surgeons, 1 clinical research coordinator, 2 sonographers, 1 medical student, and 2 undergraduate assistants. These individuals will be available to recruit and consent patients, coordinate and conduct the study, analyze the data, and produce a manuscript.

5) Study Population

Male and female adults (18 years or older) with plantar heel pain and point tenderness near the medial calcaneal insertion of the plantar fascia for at least three months without improvement will be considered for inclusion into the study. Subjects with diabetes, bilateral plantar heel pain, current systemic or local infection, previous foot surgeries, other foot/ankle pathologies (inflammatory arthritis, gout, neurologic disorders, connective tissue disorders and malignancy), contraindications to the use of NSAIDs, and pregnancy will be excluded. The target enrollment of this pilot study is 50 participants.

6) Recruitment Methods and Consenting Process

Subjects will be recruited utilizing public media, list serves, community organizations, and via referral. Please see the attachments to this application for an electronic media and brochure representations of the advertisements to be utilized. We would like to select from the following wording to produce recruitment materials -

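### The SAP compares arms on the 0-10 pain score only through a 25% responder percentage whose threshold in points changes with baseline; a baseline-adjusted comparison of the score itself is missing

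*SAP*

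**What the plan says.** The SAP (Statistical Approach, Pain Reduction) describes a "10-point pain scale range, where 0 = no pain, 1 = slight pain through 10 which equates to the patient's worst imaginable pain". The Foot Function Index paragraph that follows refers back to it: "In addition to the 11-point VAS pain scale". Each subject's result is obtained by "dividing the difference in the follow-up and baseline pain score by the baseline pain score", and the target is worded thus: "The goal for all subjects in the treatment group was to reduce pain by at least 25" per cent. The percentage meeting it is tabulated for sham and treatment arms at each follow-up. Its denominator is set "by the total number of patients that gave a pain score for that time point".

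The SAP gives no minimum baseline score, no minimum drop in points and no rule for a baseline of 0. The protocol (Section 3, Study Population) requires "plantar heel pain and point tenderness near the medial calcaneal insertion of the plantar fascia for at least three months without improvement" but sets no pain-score floor.

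Under Statistical Calculations, the SAP names Student t-tests between baseline and later measurements at alpha 0.05. It names no between-arm test. Aim 1 of the protocol is to compare patient-reported pain, function and activity between ITU and sham. The protocol's statistical paragraph does compare groups, but on FFI-P, PFCAT and FAAM scores and without baseline adjustment. It does not mention the 0-10 pain score.

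**The concern.** A percentage-of-baseline rule on a short scale sets a different hurdle in points for different subjects. Someone who starts at 4 succeeds with one step down the scale; someone who starts at 5 needs two. One step is about the size of change that can arise from ordinary variation in self-report, so subjects with low baselines can meet the goal with no real change.

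Two things are at stake. First, a chance difference between arms in the share of low baselines moves the responder percentages without any treatment effect. Second, the SAP gives the reader no other way to compare arms on this score. A within-arm test of follow-up against baseline cannot separate ITU from standard care, sham response and natural recovery, all of which act in both arms.

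**Working it through.** **Figure to reproduce.** There is none. The documents give a target of 50 subjects allocated 1:1 (about 25 per arm) and alpha 0.05. They give no power, effect size, SD or expected response rate.

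**Step 1: smallest qualifying drop.** The rule is (baseline − follow-up) / baseline ≥ 0.25, so on whole-number scores the smallest drop is 0.25 × baseline rounded up.

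| Baseline | Smallest drop (points) | As % of baseline |
|---|---|---|
| 0 | undefined (division by zero) | – |
| 1, 2, 3, 4 | 1 | 100, 50, 33.3, 25 |
| 5, 6, 7, 8 | 2 | 40, 33.3, 28.6, 25 |
| 9, 10 | 3 | 33.3, 30 |

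A subject with baseline 0 who has a follow-up score enters the denominator with no defined numerator.

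**Step 2: response with no true change.** Take follow-up as baseline plus normal error with mean 0 and SD s, rounded to a whole number. A drop of at least k points then occurs when the error falls below −(k − 0.5), with probability Φ(−(k − 0.5)/s). For k = 1 and s = 1 this is Φ(−0.5) = 0.31. The SD is an assumption, because the documents give none.

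| Assumed SD of change | Baseline 1-4 (k = 1) | Baseline 5-8 (k = 2) | Baseline 9-10 (k = 3) |
|---|---|---|---|
| 0.5 | 16% | 0% | 0% |
| 1 | 31% | 7% | 1% |
| 1.5 | 37% | 16% | 5% |
| 2 | 40% | 23% | 11% |

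Simulation with 400,000 draws per baseline gives the same figures.

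**Step 3: effect of a baseline imbalance.** Suppose one arm by chance has 5 more of its 25 subjects (20%) at baseline 1-4 rather than 5-8. The noise-only percentages then differ by 0.20 × (16 − 0) = 3.2 points at SD 0.5, 0.20 × (31 − 7) = 4.8 at SD 1, 0.20 × (37 − 16) = 4.2 at SD 1.5, and 0.20 × (40 − 23) = 3.4 at SD 2. The shift is about 3 to 5 percentage points, in either direction.

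**Step 4: precision, for illustration only.** Assume 25 per arm, control improvement 1.5 points, a further 1.5 points with ITU, SD 2, baseline mean 4 to 6, and baseline-to-follow-up correlation 0.4 to 0.6. Scores are rounded and held within 0-10, and the test is two-sided at 0.05. Simulated power is about 75-88% for ANCOVA on the score and about 43-67% if the arms were compared on responder proportions. About 4% of subjects have baseline 0 when the mean is 4, and 0.3% when it is 6.

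**The case against.** The strongest reply is that the percentage is only descriptive. The SAP attaches no test to it and does not rank it. The protocol names a computer adaptive questionnaire as the primary outcome, and its pain instruments are FFI-P and SROM. All of this stands. A reader might infer that this is the trial's headline pain result because the SAP lists it first; the documents do not say so.

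A reader might also infer that the trial loses planned power. The documents do not support that: no power is stated, no test of responder proportions is planned, and the SAP's t-tests appear to use the scores themselves. The power figures show only what would happen if arms were compared on responder proportions.

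A third tempting reading is that many unchanged subjects will be counted as successes, or that the rule favours ITU. How many depends on the baseline distribution and the measurement error, and neither is given. If nearly all subjects start at 5 or above and the SD is small, the problem almost disappears. If blinding holds, noise raises both arms alike.

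Two smaller points also stand. Any percentage rule has a threshold that rises with baseline, so the unevenness comes with the method. Baseline 0 should be rare, since entry requires persistent heel pain.

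The objection does not supply the missing comparison. A descriptive percentage plus within-arm tests still leaves the 0-10 score with no between-arm estimate.

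**Conclusion.** The point holds as an improvement to the analysis, not as an error that invalidates a result. The 1-, 2- and 3-point thresholds are exact for whole-number scoring, which the anchors and the 11-point description imply but the SAP does not state. The undefined value at baseline 0 does not depend on that assumption.

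The noise-only rates (16-40%, 0-23% and 0-11% by baseline band) rest on an assumed SD of change of 0.5 to 2 points. How far they affect the trial depends on how many subjects start at 4 or below, which the documents do not give. The likely consequences are a diluted contrast between arms and some sensitivity to chance baseline imbalance.

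The substantive gap is that the SAP gives no between-arm, baseline-adjusted analysis of a score it already collects, although Aim 1 is to compare arms.

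**What to change.** - Compare arms on the 0-10 pain score by ANCOVA with baseline score as covariate, or by a repeated-measures model across the follow-up visits with the same covariate. Report the adjusted mean difference with its 95% CI.
- Keep the 25% responder percentage by arm and timepoint, labelled as descriptive.
- State whether scores are recorded as whole numbers.
- Report how many subjects in each arm have baseline 0, and apply one stated handling rule to both arms.

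I would not add a minimum drop in points to the responder rule. The documents give no basis for a particular value, and a 2-point minimum would mean that a subject with baseline 1 could never respond.

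The cost is SAP wording and one extra model, with no new data.

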Assessment of Safety and Tolerability (Aim 3). Subject self-assessments of treatment tolerability will be conducted immediately after, two days after (phone survey) and two weeks after treatment using a 10-point visual analog scale (VAS, see Appendix 1-C). The subject will be asked to report their current level of pain and the maximum level of pain experienced over the last two days. The VAS is the standard for assessing pain for both clinical and research purposes. Recording of adverse events will take place at all visits (see adverse event reporting form Appendix 4 in the protocol). Adverse events and serious adverse events will be monitored throughout the study. A treatment will not be administered if there is residual pain/discomfort experienced by the subject from the previous treatment.

Statistical analysis. Data will be assessed for variance homogeneity and normality. FFI-P, PFCAT, and FAAM scores before and after intervention will be compared between the two groups using a paired t-test. Additionally, the mean thickness of the plantar fascia will be compared between the two groups before and after treatment and significance determined utilizing paired t tests. P<0.05 is considered to be statistically significant.

8) Risks to subjects

Exposure to ITU may produce short-term sensations which may cause discomfort and mild erythema for up to a few hours following the exposure. No detrimental side effects have been reported in previous clinical trials investigating similar devices in which ultrasound energy was applied to the neck and face. Additionally, the ITU in this investigation will utilize lower power parameters than those reported for these similar devices. We are seeking classification of the GEN II system (Guided

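### The SAP, worded as work already done, calls a 25% pain reduction the goal, but the supplied protocol text contains no pain cut-off; the SAP should cite its dated source or label it post hoc

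*SAP*

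**What the plan says.** The SAP's Pain Reduction paragraph states that "The goal for all subjects in the treatment group was to reduce pain by at least 25" per cent, measured against each subject's baseline on a 0 to 10 scale. It gives no source, rationale or date for that figure. It then reports: "The percentage of subjects that met the pain reduction goal was calculated at each timepoint for both control/sham-treated and treatment groups". On lesions it says "Hypoechoic lesions were imaged and volumes were calculated at the baseline visit and each follow-up visit", and under Statistical Calculations "Student T-tests were utilized to determine statistically significant differences between baseline and subsequent follow-up measurements for self-reported and lesion size measurements". Every data and analysis step is written as something already done. No test between arms is named for the responder percentages.

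The protocol's Statistical analysis paragraph (Section 3, item 7) looks forward: "FFI-P, PFCAT, and FAAM scores before and after intervention will be compared between the two groups using a paired t-test". It adds mean fascia thickness and, like the SAP, sets significance at 0.05. The Lay Summary names a computer-adaptive questionnaire as the primary outcome.

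**The concern.** A responder cut-off limits bias only if it was fixed before anyone saw the scores. Here the word goal implies that it was. Yet the document carrying it is written after the event, and the supplied protocol text does not contain it. If 25% had been picked because it showed ITU well against sham, the displayed difference in responder percentages would favour ITU even with no treatment effect, and a reader who took the goal as set in advance would not know to discount it.

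The concern is sharper because the outcome set also differs between the documents. The result presented as the trial's goal rests on an outcome the supplied protocol text does not define, while several outcomes that it does name are missing from the SAP.

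**Working it through.** **Text check.** There is no stated figure to reproduce: the enrolment target of 50 comes with no effect size, SD or power. The check is therefore a side-by-side reading.

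| Item | Protocol (application form) | SAP |
|---|---|---|
| Primary outcome | Computer-adaptive questionnaire (Lay Summary) | Not mentioned |
| Pain instruments for efficacy | FFI-P and SROM | 0–10 pain score; FFI pain subscale |
| 10-point VAS | Tolerability, Aim 3 | 0–10 score used for the 25% goal |
| Pain cut-off or responder rule | None | 25% reduction |
| Threshold for clinically significant change | 0.8 mm fascia thickness | Not used |
| FAAM, fascia thickness | Analysed | Not mentioned |
| Lesion | Hyperechoic; size and location recorded in long and short axis; presence or absence compared | Hypoechoic; volume from three radii, compared with baseline |
| Follow-up, weeks | 2, 4, 6, 12, 24 | 4, 8, 12, 26 |

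The FFI pain subscale is the one efficacy measure named in both documents. For lesions, measurement of size was planned. Only the volume derivation, its use as an analysed outcome and the word hypoechoic are new.

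**Illustration of what is at stake.** Inputs from the documents: 50 participants randomised 1:1, so 50 / 2 = 25 per arm. Assumptions, none of them in the documents:
- no treatment effect, complete data, one visit;
- whole-number 0–10 scores, baseline mean 6 and SD 1.7;
- follow-up mean 1 to 3 points lower, follow-up SD about 2, correlation with baseline 0.3 to 0.6;
- candidate cut-offs of 20, 25, 30, 40 and 50%.

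A responder at cut-off c has (baseline − follow-up) / baseline ≥ c. The gap is the ITU responder percentage minus the sham responder percentage. The chosen cut-off is the one with the largest gap. Each scenario used 20,000 simulated trials.

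| Quantity | 25% fixed in advance | Most ITU-favourable of five |
|---|---|---|
| Mean gap, points | 0 | about +7 to +8.5 |
| Chance of a gap ≥ 20 points | about 4–10% | 17–22% |
| False-positive rate, two-sided z-test at 0.05 | about 5–6% | about 8% |

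In patients, 0.07 × 25 = 1.75 and 0.085 × 25 = 2.1, so the inflation is about two responders in one arm. A 20-point gap is 0.20 × 25 = 5 responders. The last row of the table belongs to a test that the SAP does not plan.

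**The case against.** **Absence is not established.** The protocol supplied is an application form. Its attachment list names a separate ITU protocol dated 4/5/14, and the pain instruments are in appendices not supplied, so the 0–10 score could be part of the SROM. The SAP's opening page was also not available. An earlier dated specification may exist in any of these. This stands, and it is why the first request is for a source.

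**Past tense does not date the cut-off.** It shows when the text was worded. A goal described in the past tense is equally consistent with a goal set beforehand. This stands. A reader might infer that the cut-off was picked after the results were seen, and the documents do not support that.

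**The bias needs a motive.** Even a late choice pushes the gap towards ITU only if it was made because it favoured ITU. A choice on pooled or blinded scores, or for an outside reason, would not have that directional effect. This stands.

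**The error rate is easily overstated.** A reader might infer a false-positive rate of 15–16%. That figure counts significance in either direction at any of the five cut-offs, including results that favour sham. Choosing the most ITU-favourable cut-off gives about 8%. Moreover, the SAP's tests compare follow-up with baseline, and the five candidate cut-offs are assumed.

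**Lesion volume is not wholly new.** A reader might infer that the lesion outcome was added late. The protocol's plan to record lesion size in both axes and to compare presence or absence rules out that strong form.

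What these objections leave is a goal without a source, in a document written as a report, with the protocol's primary questionnaire, FAAM and fascia thickness missing beside it.

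**Conclusion.** The point holds in a limited form. On the text supplied, nothing lets a reader treat the 25% goal as prespecified, and the SAP does not carry forward the protocol's primary questionnaire, FAAM or fascia thickness. Data-driven choice is a possibility that has not been excluded; it has not been shown.

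The simulated inflation of the displayed gap is therefore conditional on a choice made to favour ITU, and on the assumed scores and candidate cut-offs. No size can be put on the lesion-volume part, which is the weaker half. The point does not invalidate the trial, but it should be dealt with before the 25% result is read as evidence of efficacy.

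**What to change.** 1. In the SAP's Pain Reduction and Plantar Fascia Hypoechoic Lesion Size paragraphs, cite the document, dated before data were seen, that sets the 25% goal and the lesion-volume analysis. If there is none, label both post hoc and exploratory.
2. Report the cumulative distribution of percentage change in pain by arm, with 25% as one marked point. This removes the dependence on a single cut-off, however 25% was chosen.
3. Base efficacy conclusions on the outcomes the protocol names: the computer-adaptive questionnaire, FFI-P, FAAM and fascia thickness. Add the missing ones to the SAP.
4. State whether the hypoechoic lesions in the SAP are the lesions the protocol calls hyperechoic.

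The cost is some SAP wording, one plot from pain scores already collected, and analysis of outcomes the protocol already schedules. If no dated source is found, the 25% figure can no longer be presented as a prespecified goal that was met. If one is found, the sponsor loses nothing by citing it.
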